**Protocol History:**

[figure not shown]
Initial	Version 12/21/2017	Not Activated
Amendment 1	Version 03/16/2018	Activated 06/18/2018
Amendment 2	Version 06/22/2018	Activated 08/10/2018
Amendment 3	Version 09/19/2018	Activated 04/29/2019
Amendment 4	Version 11/20/2019	Activated 04/27/2020

## SCHEMA

## STUDY SUMMARY

Endpoints: Feasibility (accrual, retention, adherence), anxiety, and depressive symptoms, cost.

Stratification Participants will be stratified by baseline score  $\geq 15$  on the GAD-7 and/or on the PHQ-9, indicating severe anxiety or depressive symptoms, and by whether they qualified for the study by the GAD-7, PHQ-9, or both.

Study Sample: 90 participants

Study Duration: 13 - 15 weeks

Brief Eligibility Criteria:

- Age  $\geq 18$  years
- Score  $\geq 10$  on the GAD-7 and/or a score  $\geq 8$  on the PHQ-9, indicating clinically significant anxiety or depressive symptoms, respectively.
- Past history of treated Stage I, II, or III (newly diagnosed or recurrent) of any of the following cancers: breast, colorectal, prostate, gynecologic (only uterine and cervical) and any stage lymphoma (Hodgkin's or non-Hodgkin's).
- 6-60 months post-treatment completion (surgery, chemotherapy, and/or radiation therapy) for cancer. Time frame applies to most recent completion of treatment if participant had a cancer recurrence. It is acceptable to be on hormonal therapies.
- Participant resides in California, Georgia, Illinois, Kansas, Michigan, Minnesota, Missouri, New Mexico, North Carolina, North Dakota, South Carolina, Virginia, Tennessee, or Wisconsin.
- Study trained therapist in state where participant resides.
- Must be able to speak and understand English.
- Must have access to a telephone.

## 1. OBJECTIVES

### 1.1 Primary Objectives

1.1.1. To determine feasibility (recruitment, accrual, retention, adherence) of a RCT of a stepped-care telehealth mental health intervention (tailored to symptom level) versus enhanced usual care in 90 post-treatment cancer survivors with moderate or severe levels of emotional distress (anxiety and/or depressive symptoms).

### 1.2 Secondary Objectives

1.2.1. To obtain preliminary data on the efficacy and variability of a stepped-care telehealth mental health intervention (tailored to symptom level) versus enhanced usual care for reducing emotional distress (anxiety and/or depressive symptoms) in 90 post-treatment cancer survivors.

1.2.2. To obtain preliminary data on the efficacy and variability of a stepped-care telehealth mental health intervention (tailored to symptom level) versus enhanced usual care for secondary outcomes (sleep disturbance, fatigue, fear of recurrence, cancer-related distress, and QOL) in 90 post-treatment cancer survivors.

1.2.3. To determine costs associated with both stepped-care telehealth and enhanced usual care interventions from the perspective of a healthcare provider. We will determine costs of intervention implementation and health care utilization in all arms over the course of the interventions.

### 1.3 Exploratory Objectives

1.3.1. To examine potential differential effects of the intervention on anxiety, depression, sleep disturbance, fatigue, fear of recurrence, and QOL, by gender, age, race/ethnicity, rural v. urban status, stratification arm (moderate, severe), and psychotropic medication use at baseline.

1.3.2. To examine mediating effects of expectancy ratings of the intervention on anxiety and depression.

## 2. BACKGROUND

### 2.1 Distress in Cancer Survivors

Psychological concerns are among the most commonly reported unmet needs among post-treatment cancer survivors. Psychosocial distress, including anxiety and depressive symptoms, is also common. Up to 54% of post-treatment cancer survivors report clinically significant distress, which is associated with multiple adverse outcomes, including decreased quality of life (QOL), functional limitations, poor sleep, increased pain, and – particularly for those with elevated depressive symptoms – increased mortality. The Institute of Medicine has emphasized post-treatment survivorship as a “distinct phase of cancer care,” with a need for ensuring delivery of appropriate care for cancer survivors. The need for interventions to reduce psychosocial morbidity in post-treatment cancer survivors is critical. Psychosocial interventions for post-treatment cancer survivors may improve mental and physical health, potentially offsetting increased health care costs among distressed cancer survivors.

Mental health issues are more prevalent among the 2.8 million US cancer survivors living in rural (versus non-rural) areas, further illustrating how the “burden of cancer is magnified among the US rural population.” Rural cancer survivors report more mental health concerns than non-rural cancer

survivors, yet psychosocial care for cancer survivors is scarce in many rural areas. Almost 21% of U.S. cancer survivors reside in rural areas, and over half of rural counties have no mental health professionals. Recent studies found poorer accessibility to mental health professionals and higher levels of unmet needs in rural cancer survivors. Interventions that are accessible to post-treatment cancer survivors experiencing significant distress may reduce this cancer health disparity.

## 2.2 Rationale

Noting the need for evidence-based cancer survivorship care, the American Society of Clinical Oncology (ASCO) published guidelines for screening, assessment, and care of psychosocial distress (anxiety, depression) in adults with cancer. These guidelines recommend screening all adults with cancer for distress and treating those with moderate or severe symptoms using a stepped-care approach tailored to distress severity. While these guidelines apply to survivors with all cancer types across the cancer treatment and survivorship continuum, we have chosen to focus on survivors with non-metastatic breast, colorectal, prostate, uterine, and cervical cancers, as well as those with any stage lymphoma (Hodgkin's or non-Hodgkin's). Further, we have focused on the post-treatment survivorship period 6 months-5 years post-treatment because distress may be more likely to be assessed and addressed after treatment completion. A significant minority of post-treatment survivors is at risk for anxiety and depression symptoms during the five years following the end of treatment and accessible interventions are needed to treat them.

The purpose of this study is to test a method of implementing this stepped-care approach in community oncology practices caring for cancer survivors, using self-directed and stepped-care telehealth approaches based on cognitive-behavioral theory. Our approach is based on a previous trial of telephone-based cognitive behavioral therapy for rural older adults with Generalized Anxiety Disorder (NIMH 1R01MH083664: The Tranquil Moments Study; PI: [name]), which has demonstrated high acceptability and efficacy for reducing anxiety, worry, and depressive symptoms in a rural geriatric population. This protocol adapts the methods of the previous trial to bring psychosocial care to underserved cancer survivors, many of whom have minimal or no access to mental health providers. Cancer survivors will be recruited through multiple NCI Community Oncology Research Program (NCORP) sites through the NCI-funded Wake Forest NCORP Research Base (WF NCORP RB).

We will obtain data on feasibility, outcome variability, and efficacy for designing a subsequent fully powered randomized controlled trial (RCT) assessing the effects of the intervention on distress in cancer survivors. In the planned larger study, we anticipate that this intervention will: (a) reduce treatment barriers for post-treatment cancer survivors; (b) enhance availability of psychosocial treatment (through use of telephone sessions and a workbook); and (c) result in reductions in anxiety and depressive symptoms in cancer survivors.

## 3. SUMMARY OF STUDY PLAN

This study compares a stepped-care telehealth intervention (tailored to level of symptomatology and designed to reduce anxiety and depressive symptoms) with enhanced usual care (EUC). Participants with no/mild symptoms will be provided survivorship resources and will not be included in the trial.

A total of 90 participants will be randomized. Study screening will be completed by a Research Nurse or an appropriate designated research staff member at each NCORP component. Assuming an accrual rate of approximately 8-9 randomized participants per month, we expect study recruitment to be complete within 11 months.

Referred participants will waive documentation of informed consent to complete the PHQ-2 and single anxiety question. If a participant scores  $\geq 2$  on the PHQ-2 or  $\geq 1$  on the anxiety question, he/she will be invited to complete the full screening assessment to determine study eligibility. The participant will complete the Abbreviated Verbal Consent at this point. We are asking to waive the following elements of

consent for this second step of screening: disclosure of appropriate alternatives, statements regarding who may access the participant's medical record for verification, and compensation for injury. If they meet all eligibility criteria and want to participate in the randomized trial, they will provide full informed consent for study participation. Trained research staff members at each NCORP component will obtain full informed consent from all interested and eligible potential participants.

In accordance with ASCO guidelines, participants with no/mild symptoms will be provided with written survivorship resources (a letter that contains a link to the National Cancer Institute booklet "Facing Forward: Life after Cancer Treatment") and will not be randomized (Appendix 20). Participants with either moderate or severe distress (anxiety or depressive symptoms) will be randomized into stepped-care telehealth (tailored to level of symptoms) or EUC. For participants with moderate symptoms (PHQ-9: 8-14; GAD-7: 10-14), low-intensity stepped-care telehealth will consist of a self-guided cognitive behavioral therapy (CBT) workbook to reduce anxiety and depressive symptoms and biweekly (every two weeks) check-in calls from research staff at NCORP components. On the biweekly check-in calls, research staff from NCORP components will provide minimal support and will administer the scripted "Telephone Script/Manual for Low-Intensity Group Check-in Call Form." This form assesses changes in symptom severity during the past two weeks. The site staff person is directed to follow Telehealth crisis protocol, refer to Appendix 21, for participants indicating "thoughts of death or suicidal ideation." Site staff should also follow crisis procedures for any other problems identified during administration of the form where follow-up is needed.

For participants with severe symptoms (PHQ-9: 15-27; GAD-7: 15-21), high intensity stepped-care telehealth will consist of a CBT workbook with accompanying psychotherapy by a Master's- or doctoral-level therapist delivered by telephone. Participants randomized to EUC will receive survivorship resources (Appendix 20) and referral information for local mental health providers.

## **4. PARTICIPANT SELECTION**

### **4.1 Inclusion Criteria**

- 4.1.1.** Age  $\geq 18$  years
- 4.1.2.** Score  $\geq 10$  on the GAD-7 and/or a score  $\geq 8$  on the PHQ-9, indicating clinically significant anxiety or depressive symptoms, respectively.
- 4.1.3.** Past history of treated (newly diagnosed or recurrent) breast, colorectal, prostate, gynecologic (only uterine and cervical) cancers (Stage I, II, or III) or any stage lymphoma (Hodgkin's or non-Hodgkin's).
- 4.1.4.** 6-60 months post-treatment (surgery, chemotherapy, radiation therapy, and/or maintenance therapies) for cancer. Time frame applies to most recent completion of treatment if participant had a cancer recurrence. It is acceptable to be on hormonal therapies.
- 4.1.5.** Participant resides in California, Georgia, Illinois, Kansas, Michigan, Minnesota, Missouri, New Mexico, North Carolina, North Dakota, South Carolina, Virginia, Tennessee, or Wisconsin.
- 4.1.6.** Study-trained therapist in the state where the participant resides.
- 4.1.7.** Must be able to speak and understand English.
- 4.1.8.** Must have access to a telephone. If a patient does not have access to a phone or has difficulty paying for minutes for a mobile phone, the research team should contact the Wake Forest investigators or site coordinators to arrange for assistance.

## 4.2 Exclusion Criteria

- 4.2.1.** Current psychotherapy [regular appointment(s) with a psychologist, counselor, or therapist within the last 30 days prior to randomization]
- 4.2.2.** Self-reported active alcohol or substance abuse within the last 30 days
- 4.2.3.** Past history of prostate cancer or non-Hodgkin's lymphoma with only active surveillance (i.e., no surgery, chemotherapy, or radiation therapy)
- 4.2.4.** Progressive cancer (must be considered no evidence of disease or stable)
- 4.2.6.** Self-reported psychotic symptoms in the last 30 days prior to randomization (See item in Appendix 4: "Have you seen things that aren't really there or have you heard voices when no one else was around within the last 30 days?")
- 4.2.7.** Active suicidal ideation with plan and intent
- 4.2.8.** Any change in psychotropic medications within the last 30 days (See Appendix 25)
- 4.2.9.** Hearing loss that would preclude participating in telephone sessions (determined by brief hearing assessment administered by research staff at each NCORP component). Individuals who can compensate for hearing loss through the use of a hearing device or TDD phone, and through the use of such devices are able to communicate with the study therapist by telephone, will be included. If the therapist cannot communicate with the participant by telephone, the participant will be excluded.
- 4.2.10.** Failure/inability/unwillingness to provide names and contact information for two family members or friends to serve as emergency contacts during the course of the study

## 4.3 Inclusion of Women and Minorities

Both men and women (as applicable) and members of all races and ethnic groups are eligible for this trial.

	Females	Males	Total
Ethnic			
Hispanic	8	7	15
Not Hispanic	40	35	75
ETHNIC TOTAL	48	42	90

	Females	Males	Total
Racial			
Am Indian	1	0	1
Asian	2	1	3
Native Hawaiian	0	0	0
Black	6	9	15
White	39	32	71
RACIAL TOTAL	48	42	90

#### **4.4 Recruitment and Retention Plan**

Participants will be followed for 13 - 15 weeks. After the Week 13 visit (for participants in the intervention group, Week 13 measures should be completed after the intervention is finished and could be Weeks 13 – 15), the participant is no longer followed and data are no longer collected from the participant.

NCORP sites will accrue to this trial through the National Cancer Institute NCORP program. The WF NCORP RB will sponsor and administer this trial. There will be a secure, password protected TELEHEALTH study website for the management of study participants including randomization, schedule of study visits and data entry of forms designated to be entered by site staff. Data reports and documents will also be available.

Potential participants may be recruited via (1) in-clinic screening during medical appointments; (2) identifying survivors through the site cancer registry; (3) screening clinic charts; and (4) participant recruitment flyers (Support Document 5) and recruitment letters (Support Document 4). Local sites should check with their IRBs to determine if a partial HIPAA waiver is required for the review of participant medical records/charts. Survivors will be approached in-person or by telephone by NCORP staff to ascertain interest and initial eligibility. We will track numbers of survivors approached and screened, reasons for nonparticipation, and number randomized. All written materials will be at an 8th grade reading level.

We expect to recruit minority participants through several strategies. (1) We will request review of our protocol and recruitment materials from the Wake Forest Baptist Comprehensive Cancer Center Cancer Office of Cancer Health Equity (for whom [name] serves as an Assistant Director) and the Wake Forest NCORP Research Base (WF NCORP RB) for suggestions to enhance the appeal of our study to minority participants. (2) We will inform all Minority-Underserved NCORPs affiliated with the WF NCORP RB in targeted states about the study and seek their feedback on how to enhance minority recruitment. Working with [name], PI of the WF NCORP RB, we will additionally reach out to Minority-based NCORPs not currently affiliated with Wake Forest, but with components/sub-components in targeted states and encourage them to participate in this study. (3) We will emphasize the importance of robust minority accrual at our study kickoff meetings and provide specific education and discussion about strategies to overcome barriers that underserved patients may experience to study participation. (4) We will monitor minority recruitment rates at our monthly WF NCORP RB executive committee meetings and provide feedback to the NCORP sites via bimonthly study teleconference calls. Specifically, we will monitor the minority recruitment rate in conjunction with available data about the population of eligible patients at the site to identify sites that are potentially under-performing with regard to minority accrual. Sites with strong minority recruitment will be asked to share their experiences with other sites during these calls.

Several elements of this trial were designed with retention in mind. First, the follow-up period is brief, with total study enrollment lasting only 13 – 15 weeks. Second, the stepped-care telehealth group will receive weekly or biweekly (every two weeks) calls from research staff at NCORP components or therapists. We will send thank-you letters to the enhanced usual care group following their assessments at baseline and 7 weeks (Support document 6). Finally, if a participant does not have a telephone or is unable to purchase minutes for their mobile phone to participate in the study intervention or assessments, the research team should contact the Wake Forest investigators or site coordinators to arrange for assistance.

## **5. INTERVENTION PARAMETERS (RETENTION, ADHERENCE, TREATMENT FIDELITY)**

### **5.1 Study retention**

Study retention will be estimated by the proportion of participants who complete the Week 7 and 13 visits.

### **5.2 Adherence**

Adherence will be recorded as the percentage of therapy sessions (for the high-intensity intervention group) or check-in calls (for the low-intensity intervention group) each participant completes.

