High Intensity Stepped-care Telehealth: The high-intensity stepped-care telehealth group will consist of the CBT workbook (15 minutes daily to complete exercises/homework), plus psychotherapy delivered by telephone with a licensed therapist (45 minute sessions weekly). If participant is randomized to the High

Intensity Arm, the therapist will make at least one attempt to schedule the participant's first therapy session within 2 weeks of the date of notification via email.

Consistent with the ASCO guidelines, the Wake Forest NCORP Research Base staff will mail a professionally prepared and IRB approved CBT workbook to participants and participants will have 12 weekly therapy sessions with the study therapist. The study therapist will be a licensed mental health provider (e.g., licensed clinical social worker, marriage and family therapist, licensed professional counselor, psychologist). Onsite or phone training is provided for all participating therapists. Training will include the use of the workbook, formal didactic presentations, readings, and role-plays. All study therapists will receive regular (at least monthly) study supervision from [name]. There will be at least one trained therapist for each state in the U.S. that has any participating sites. Each week, the participant will receive one 45-minute telephone session and one workbook chapter. The sessions will supplement the participant's understanding of anxiety, depression, and distress management techniques and include a review of the daily workbook exercises to assure understanding and maximize application in daily life.

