## 8. CRITERIA FOR EVALUATION AND ENDPOINT DEFINITION

### 8.1 Primary Endpoint

To determine study feasibility, recruitment, accrual, retention, and adherence rates will be calculated as follows:

**Recruitment.** To determine recruitment rate, we will track number of individuals who met all eligibility criteria and percent who agree to participate.

**Accrual.** Accrual rates will be calculated by calculating the mean number of participants recruited per month.

**Retention.** Study retention will be estimated by the proportion of participants who complete the Week 13 visit. Drop-out is defined as 100% minus the dropout %.

**Adherence.** Intervention adherence will be estimated as the mean percentage of therapy (high-intensity intervention) or check-in (low-intensity intervention) sessions each participant completes.

The Working Alliance Inventory will be summarized with descriptive statistics to describe the therapist-participant relationship as a process measure

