### **13.2 Randomization/Stratification**

Participants will be stratified by baseline score  $\geq 15$  on the GAD-7 and/or on the PHQ-9, indicating severe anxiety or depressive symptoms, and by whether they qualified for the study by the GAD-7, PHQ-9, or both. Participants with moderate symptoms only (8-14 on the PHQ-9 and  $< 15$  on the GAD-7 or 10-14 on the GAD-7 and  $< 15$  on the PHQ-9) will be randomized to either the low-intensity stepped-care telehealth or to the enhanced usual care (EUC control) with equal probability. Participants with severe symptoms will be randomized to either the high-intensity stepped-care telehealth intervention or the EUC control with equal probability. Participants randomized to the low-intensity stepped care telehealth arm who experience increased symptoms at week seven and now experience severe level of symptomatology will receive the high-intensity intervention (see Section 7.1). Analysis will proceed as intent-to-treat using

their initial stepped-care telehealth assignment; we do not anticipate that many people will change from moderate to severe during the study. We anticipate enrolling 45 patients in the stepped-care telehealth intervention and 45 in the enhanced usual care group. We will enroll 50 participants in the moderate symptom strata, and 40 participants in the severe symptom strata. Block sizes will be chosen randomly to ensure that future assignments cannot be inferred from previous ones.

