### 13.3 Sample Size

The sample size (N=90) is based on goals of estimating retention, recruitment, adherence and accrual rates and effect sizes to inform design of a larger efficacy trial. If the drop-out rate is  $>30\%$ , a larger study may not be feasible. With N=90, we are confident that this rate will be  $\leq 30\%$  when the observed drop-out rate is as large as 22% (upper limit of the one-sided 95% CI is 29.2%). Similarly, the lower limit of a one-sided 95% confidence interval for the recruitment rate can be estimated within 8.2% of the observed rate if we approach at least 100 participants to recruit 90, and the lower limit of a one-sided 95% confidence interval for the adherence can be estimated within 8.7% of the observed rate with N=90. Using the normal approximation to the Poisson, we can estimate the lower limit of the one-sided 95% confidence interval of the accrual rate within approximately 2 people per month if the observed rate is 11 people per month. To compare differences between the groups on changes in the PHQ-9 and GAD-7 scores, we can estimate the intervention effect within  $\pm 0.46$  SD with a sample size of 36/group (stepped-care telehealth, enhanced usual care), allowing 20% dropout of the 45/group randomized. This corresponds to 2.7 points on PHQ-9 and 1.9 points on GAD-7 using SDs from studies of change in the measures of 5.8 and 4.2 points, respectively.

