### 13.4 Primary Objective, Endpoint(s), Analysis Plan

For Objective 1.1.1, recruitment, accrual, retention, and adherence rates will be calculated. To determine the recruitment rate, we will track number of eligible participants and percent who agree to participate. Accrual rates will be calculated by calculating the mean number of participants recruited per month. Study retention will be estimated by the proportion of participants who complete the Week 7 and 13 visits. Intervention adherence will be estimated as the mean percentage of therapy or check-in sessions each participant completes. Drop-out is defined as 100% minus the dropout %. 95% confidence intervals will be calculated for each measure to quantify uncertainty in the estimates and to determine if the lower (recruitment, accrual) or upper (retention, adherence) limit would indicate lack of feasibility for future work.

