### **13.7 Reporting and Exclusions**

Unless we receive written or verbal withdrawal of consent, we will try to reach every participant for telephone calls, telephone sessions, and assessments as outlined in the protocol.

The dataset used in the analysis of Objective 1.1.1 will include all eligible participants to calculate recruitment rates. Accrual, retention, and adherence will be calculated on the participants who consent to participate in the study. The analysis of the secondary objectives and exploratory objective will include all participants who consent to participate in the study. The ANOVA models used for the secondary objectives use data from all available time points and allows for data to be missing at random. For the analyses of the secondary objectives and the exploratory objective, we will use an intent-to-treat approach. If participants are moved from low intensity to high intensity they will be analyzed using the

low intensity assignment (intent to treat). In exploratory models, we will analyze the impact of adherence by including it as a predictor.

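### Primary adherence is summarised as one mean over therapy sessions or check-in calls, with no estimate planned by intensity level, and its 8.7% margin counts 90 participants when only about 45 have contacts to attend

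*Combined protocol and SAP*

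**What the plan says.** Adherence is one of four primary feasibility measures (1.1.1, 8.1, 13.1.1). Section 5.2 defines it per participant, on a different contact for each level: the "percentage of therapy sessions (for the high-intensity intervention group) or check-in calls (for the low-intensity intervention group) each participant completes". Section 8.1 gives the endpoint: "Intervention adherence will be estimated as the mean percentage of therapy (high-intensity intervention) or check-in (low-intensity intervention) sessions each participant completes". Section 13.4 repeats it without naming the levels: "Intervention adherence will be estimated as the mean percentage of therapy or check-in sessions each participant completes". Section 13.3 gives one precision figure: "the lower limit of a one-sided 95% confidence interval for the adherence can be estimated within 8.7% of the observed rate with N=90". Section 13.7 gives one analysis set: "Accrual, retention, and adherence will be calculated on the participants who consent to participate in the study".

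The two contacts differ. For high intensity, 7.1 states that "participants will have 12 weekly therapy sessions with the study therapist", each lasting 45 minutes. For low intensity, 7.1 describes staff calls of 5-10 minutes, and the Study Parameter Table in 7.9 places them at weeks 2, 4, 6, 8, 10 and 12, which makes six.

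Section 13.2 randomises each level against EUC, with equal probability, inside its own severity stratum: "We will enroll 50 participants in the moderate symptom strata, and 40 participants in the severe symptom strata".

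No section plans an adherence mean or interval by level. The analysis by stratification arm in 13.6 covers only the outcomes of Objectives 1.2.1 and 1.2.2. By contrast, 13.5 does separate the levels for the combined depression/anxiety outcome and for costs.

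**The concern.** Completing a weekly therapy session with a licensed therapist and answering a short scripted call are different behaviours in different interventions. One average over both lets high call completion offset poor therapy attendance, and therapy is the therapist-dependent component. Section 2.2 says the feasibility data are meant to design a fully powered trial. A mean tied to this study's 50/40 quota carries over only if the later trial has the same severity mix or both levels adhere equally.

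The precision statement has a separate fault. About half of the 90 participants are in EUC and have neither sessions nor calls, so a margin computed on 90 is not the precision of any adherence estimate, overall or by level.

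**Working it through.** **Inputs.** Strata of 50 moderate and 40 severe, equal allocation within stratum, and 45 per arm (13.2). This gives about 25 low-intensity and 20 high-intensity participants, or 45 with contacts to attend. The stated margin is 8.7%, one-sided 95%, N=90 (13.3).

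**Reproducing the plan's figure.** The half-width is 1.645 × √(p(1−p)/n). The plan does not state p. With p = 0.5 and n = 90, 1.645 × √(0.25/90) = 0.0867, or 8.7 points. The two-sided version gives 10.3 and does not match. The same one-sided formula also returns the other figures in 13.3:
- drop-out limit: 0.22 + 1.645 × √(0.22 × 0.78/90) = 29.2%
- recruitment margin: 1.645 × √(0.25/100) = 8.2 points

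**Same formula, participants who have contacts.**

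| Group | n | One-sided 95% margin, p = 0.5 |
|---|---|---|
| All stepped care | 45 | 12.3 points |
| Low intensity | 25 | 16.4 points |
| High intensity | 20 | 18.4 points |

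These are upper bounds. A percentage between 0 and 100 with mean p has variance of at most p(1−p), itself at most 0.25. If participant percentages had an SD of 30 points (assumption), the margins would be 1.645 × 30/√n = 7.4, 9.9 and 11.0 points for n = 45, 25 and 20.

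**Weights in a single mean.** Each participant counts once, so the weights are 25/45 = 55.6% low and 20/45 = 44.4% high.

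**Masking (assumed rates).** With calls at 95% and therapy at 55%: (25 × 95 + 20 × 55)/45 = 77.2%. In reverse, an overall 80% fits therapy attendance of (0.80 × 45 − 0.90 × 25)/20 = 67.5% if calls are at 90%, and (0.80 × 45 − 1.00 × 25)/20 = 55% if calls are at 100%.

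**Dependence on mix (same assumed rates).** An even split gives (95 + 55)/2 = 75.0%, about 2 points below 77.2%. If both levels adhere equally, the mix has no effect.

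**Participants moved at Week 7.** Sections 7.1 and 13.2 allow a move from low to high intensity, analysed by initial assignment. The adherence denominator after a move is not defined. Someone who took the three calls due at weeks 2, 4 and 6 and was then moved would score 3/6 = 50% against a fixed six, but 3/3 = 100% against calls due before the move.

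**The case against.** **Pooling is not stated.** Section 5.2 does no averaging, and 8.1 names both levels, so it could be read as one mean per level. This stands in part. A single mean is the natural reading, given the wording of 13.4, one margin in 13.3 and one analysis set in 13.7, but it is an inference. The 8.7% is weak support for it, because N=90 fits neither reading. Either way, the text needs to say which is meant.

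**An overall figure suits the objective.** Objective 1.1.1 concerns one stepped-care programme tailored to symptom level, so an overall mean is a legitimate summary. That stands as a reason to keep one, but not as a reason to omit the level-specific figures.

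**Little is lost.** The contacts are recorded on separate forms (Appendices 14 and 16), so a split can always be tabulated. True, but without prespecification it becomes a post hoc choice on a primary measure.

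**Stronger readings that the documents do not support.** A reader might infer that 12 sessions against 6 calls distorts the weighting. It does not, because the endpoint averages participant percentages and the counts drop out. A reader might also infer a large swing from case mix: at the assumed rates, an 80:20 moderate-to-severe mix gives 87% and a 30:70 mix gives 67%. That 20-point range needs assumed rates and extreme mixes, and the documents give no expected mix for the later trial.

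**Conclusion.** The concern holds for a primary feasibility measure, on two counts. First, adherence is summarised without any planned estimate by level, although the levels are different interventions randomised in separate strata. On the natural reading, the single mean can hide low therapy attendance; the 77% example shows how, but its 95% and 55% rates are assumptions. Near the planned mix, the dependence on case mix is small.

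Second, the 8.7-point margin is wrong for adherence whichever reading is taken. It reproduces only with n = 90, while about 45 participants can adhere to anything. On the plan's own worst-case basis the figures are 12.3 points overall, 16.4 for low intensity and 18.4 for high intensity, assuming the 25:20 split implied by 13.2.

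A reader might conclude that masking would reverse a feasibility decision. The documents do not allow that: 13.4 says a confidence limit will be used to judge feasibility, but no adherence threshold is given. The only numerical criterion in 13.3 is for drop-out.

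**What to change.** **Sections 8.1 and 13.4.** Report mean adherence with a 95% interval separately for high intensity (therapy sessions) and low intensity (check-in calls), by initial assignment. Give any overall stepped-care mean as secondary, with its severity mix stated. For participants moved at Week 7, count low-intensity adherence against the calls due before the move.

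**Section 13.3.** Replace the 8.7% (N=90) with margins based on stepped-care participants only: 12.3 points overall (n=45), 16.4 for low intensity (n=25) and 18.4 for high intensity (n=20). Label them as upper bounds at p = 0.5, one-sided 95%, because adherence is a mean of participant percentages.

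**Cost.** Wording only; the data are already collected by level. The downside is that the stated margins become wider.
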